14 CENTRAL REVIEW PROCEDURES AND TISSUE COLLECTION

14.1 Central Radiology Review

Central radiology review of equivocal cases by a review committee may be conducted. A retrospective radiology review of all cases may also be undertaken.

14.2 Central Pathology Review

This central pathological review includes the pre-treatment biopsy with sending of one representative HES section and paraffin bloc. All slides of tumor and nodes must also be sending.

14.3 Tissue Collection

Tissue collection for pre-treatment (one block, frozen tumor if available) and post treatment (fresh tumor and normal tissue, formalin fixed, paraffin embedded and frozen tumor and node tissue if available) is mandatory from existing tumour specimens be submitted to a central reference laboratory for analysis.

The tissue may be used by researchers now or in the future to better understand the nature of non-small cell lung cancer and how patients respond to treatments. Samples will be used for research purposes only and will not be sold. A scientific review process of any proposals to use the tissue will take place and any proposals approved will have undergone ethics approval. Patients will not be identified by name. The only identification of tissue will be by a patient study number assigned at the time of registration to the trial the surgical/ histology number and/or patient initials. Material issued to researchers will be anonymized and only identified by a coded number. This process is applicable to all tissues collected as part of this study, irrespective of the location of the Tissue/Tumour Bank (see Section 13.3.5).

Testing specifically for hereditary genetic defects predisposing to malignant disease will not be carried out without the expressed consent of the patient.

All patients on whom a diagnostic tumour block is collected will be aware of this retrieval and will have given their consent.

14.3.1 Serum and plasma

Serum and plasma will be collected before first infusion and after 3rd infusion of durvalumab.

Anti-tumour immune responses are key contributors to the anti-tumour effects of anti-PD-L1 therapies. Serological responses (cytokines, antibodies and metabolites) provide rich sources of correlative data that can be used to understand the biological consequences of this novel therapy and may provide important biomarkers that will facilitate future patient management.

13.3.2 Feces

Feces will be collected before first infusion of durvalumab.

Currently, only few parameters have been identified as predictive biomarker of response, such as positive expression of PD-L1, and high mutational loads of tumors that appears to be associated with a higher response rate to anti-PD1 mAb. New lines of evidence demonstrated the biological significance of the gut microbiome (diverse range of symbiotic microorganisms) has an important contributor of pulmonary pathologies such as asthma and COPD (see APPENDIX V).

14.3.2 Tumour and Tissue Banks

Blocks and all other samples will be carefully banked at the IFCT Repository.

14.3.3 Translational study

See Appendix V

15 STATISTICAL CONSIDERATIONS

15.1 Objectives and Design

This is a multi-centre, prospective unblinded, single-arm phase II trial of the human monoclonal antibody directed against programmed cell death ligand-1 (PD-L1) durvalumab in neoadjuvant treatment in primary resectable stage IB (only T = 4 cm in greatest dimension, N0), stage IIA (T2b,N0) and some of stage IIB : (T1-2,N1) and (T3 : > 5 cm and \leq 7 cm in greatest dimension surrounded by lung or associated with separate tumor nodule(s) in the same lobe but without mediastinum or chest wall involvements, or superior sulcus tumors, N0) non-small cell lung cancer patients.

The primary objective is surgical resection R0 after maximum 3 cycles of immune therapy.

Secondary objectives will evaluate study treatment effect:

- Response Rate (RECIST 1.1) and metabolic response rate on TEP-FDG
- Tolerance and Post-operative adverse events (30 days after surgery)
- Delay between surgery and start of treatment
- Evaluation of predictive/prognostic significance of PD-1/PD-L1 expression
- Disease Free Survival (DFS)
- Overall survival (OS)
- Evaluation of changes in plasma/serum cytokines and other biomarkers before and after treatment
- Major Pathological Response on surgical tissue

15.2 Sample Size, Power

The maximum sample size (N) is calculated based on α , β , and the expected effect size, using a test for single binomial proportion for a two-stage design with a 1:1 randomization and O'Brien-Fleming (OF) stopping rules, allowing for early stopping for futility after Stage I. The software East 6.0 was used.

The rate of complete resection equal to or lower than 85% (P0) is considered as unacceptable after immune treatment. On the other hand, we can conclude to a good rate of complete resection if it is 95% (P1). The computation is based on the following assumption, considering the probability of compliance: P0 =85%; P1 = 95%; statistical power of 0.90; type I error rate (one-sided) of 0.05.

The null hypothesis that the rate of complete resection is P0 = 85% will be tested against a one-sided alternative. In the first stage, 39 patients will be accrued. If there are 34 or fewer responses in these 39 patients, the study will be stopped for futility. Otherwise, 38 additional patients will be accrued for a total of 77. The null hypothesis will be rejected if 71 or more responses are observed in 77 patients. To take into account 5% of ineligible patients, 81 patients will be included.

Duration of accrual: 18 months and 1 year follow-up.

15.3 Analysis population

- The population of tolerance is defined as all patients who received one dose of treatment

- The population the intent to treat (ITT) will include all patients included
- The population of eligible patients will consist of ITT patients presenting no deviation judged major on the criteria for inclusion and non-inclusion

The deviations to the protocol will be reviewed by the principal investigators and then classified into minor or major deviations, and listed.

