5.1 Eligibility Criteria

There will be NO EXCEPTIONS to eligibility requirements at the time of inclusion. Questions about eligibility criteria should be addressed prior to inclusion.

The eligibility criteria for this study have been carefully considered. Eligibility criteria are standards used to ensure that patients who enter this study are medically appropriate candidates for this therapy.

Patients must fulfil all of the following criteria to be eligible for admission to the study:

- 1 Histologically confirmed diagnosis of primary non-small cell carcinoma of the lung.
- 2 Tissue block of diagnosis must be available for submission after inclusion (one HES slide and one paraffin embedded block).
- 3 Patients must be classified clinically as Stage IB (only T = 4 cm in greatest dimension, N0), Stage IIA (T2b,N0) and some of Stage IIB : (T1-2,N1) and (T3 : > 5 cm and ≤ 7 cm in greatest dimension surrounded by lung or associated with separate tumor nodule(s) in the same lobe but **without** mediastinum or chest wall involvements, or superior sulcus tumors, N0) on the basis of clinical evaluation (8th classification TNM, UICC 2015). In case of invasion of the main bronchus (distance < 2 cm from carina), a biopsy of the carina is required. A pre-surgical PET scan of the thorax and a MRI or CT scan of the brain as well as thorax abdomen pelvis CT scan must be done prior to surgery and before inclusion. **If preoperative CT and/or PET are suspicious for mediastinal nodal involvement, invasive mediastinal staging with mediastinoscopy or EBUS-TBNA must be performed.** Station 5 or 6 lymph nodes may be accessed by anterior mediastinotomy or VATS.
- 4 Pre-operative (neo-adjuvant) platinum based or other chemotherapy except the treatment of the protocol is not permissible. Pre-operative radiation therapy is not permissible
- 5 The patient must have an ECOG performance status of 0, 1.
- 6 Hematology (done within 14 days prior to inclusion and with values within the ranges specified below):
If anemic, patients should be asymptomatic and should not be decompensated. Transfusions are permissible.

Haemoglobin ≥ 9,0 g/dL

Absolute neutrophil count ≥ $1.5 \times 10^9/L$ or ≥ 1,500/ μ l

Platelets ≥ $100 \times 10^9/L$ or ≥ 100,000/ μ l

- 7 Biochemistry (done within 14 days prior to inclusion and with values within the ranges specified below):

Total bilirubin* within normal institutional limits

Alkaline phosphatase ≤ 2.5 x institutional upper limit of normal

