AST(SGOT) and ALT(SGPT) ≤ 2.5 x institutional upper limit of normal

Creatinine Clearance ≥ 40 ml/min

TSH

within normal institutional limits

* *excluding Gilbert's syndrome*

Creatinine clearance to be measured directly by 24 hour urine sampling or as calculated by Cockcroft Formula:

$$\text{Females: GFR} = \frac{1.04 \times (140 - \text{age}) \times \text{weight in kg}}{\text{serum creatinine in } \mu\text{mol/L}}$$

$$\text{Males: GFR} = \frac{1.23 \times (140 - \text{age}) \times \text{weight in kg}}{\text{serum creatinine in } \mu\text{mol/L}}$$

- 8 Other investigations detailed in Section 6 must have been performed within the timelines indicated.
- 9 Patient consent must be appropriately obtained in accordance with applicable local and regulatory requirements. Each patient must sign a consent form prior to inclusion in the trial to document their willingness to participate.
- 10 Patients must be accessible for treatment and follow-up. Investigators must assure themselves the patients included on this trial will be available for complete documentation of the treatment, adverse events, and follow-up.
- 11 Protocol treatment is to begin within 7 days of patient inclusion.
- 12 Age of at least 18 years.
- 13 Female subjects must either be of non-reproductive potential (ie, post-menopausal by history: ≥ 60 years old and no menses for ≥ 1 year without an alternative medical cause; OR history of hysterectomy, OR history of bilateral tubal ligation, OR history of bilateral oophorectomy) or must have a negative serum pregnancy test upon study entry.
- 14 Females of childbearing potential who are sexually active with a non-sterilized male partner or men who are sexually active with women of childbearing potential must use a highly effective method of contraception prior the first dose of investigational product, and must agree to continue using such precautions for 4 months after the final dose of investigational product. Periodic abstinence, the rhythm method, and the withdrawal method are not acceptable methods of contraception.

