5.2 Ineligibility Criteria

Patients who fulfil any of the following criteria are not eligible for admission to the study:

- 1 Patients with a history of other malignancies, except: adequately treated non-melanoma skin cancer, curatively treated in-situ cancer, or other solid tumours curatively treated with no evidence of disease for ≥ 5 years following the end of treatment and which, in the opinion of the treating physician, do not have a substantial risk of recurrence of the prior malignancy.
- 2 A combination of small cell and non-small cell lung cancer or pulmonary carcinoid tumour.
- 3 History of autoimmune disease, including but not limited to myasthenia gravis, myositis, autoimmune hepatitis, systemic lupus erythematosus, rheumatoid arthritis, inflammatory bowel disease, vascular thrombosis associated with antiphospholipid syndrome, Wegener's granulomatosis, Sjögren's syndrome, Guillain-Barré syndrome, multiple sclerosis, vasculitis, or glomerulonephritis. NOTE: patients with Grave's disease and/or psoriasis not requiring systemic therapy within the last two years from inclusion are not excluded.

4 History of primary immunodeficiency, history of allogenic organ transplant, use of immunosuppressive agents within 28 days of inclusion* or a prior history of severe (grade 3 or 4) immune mediated toxicity from other immune therapy.

* *NOTE: Intranasal/inhaled corticosteroids or systemic steroids that do not to exceed 10 mg/day of prednisone or equivalent dose of an alternative corticosteroid are permissible.*

5 Live attenuated vaccination administered within 30 days prior to inclusion.

6 History of hypersensitivity to durvalumab or any excipient.

7 Patients who have experienced untreated and/or uncontrolled cardiovascular conditions and/or have symptomatic cardiac dysfunction (unstable angina, congestive heart failure, myocardial infarction within the previous year or cardiac ventricular arrhythmias requiring medication, history of 2nd or 3rd degree atrioventricular conduction defects). Patients with a significant cardiac history, even if controlled, should have a LVEF > 50% within 12 weeks prior to inclusion.

8 Concurrent treatment with other investigational drugs or anti-cancer therapy.

9 Patients with active or uncontrolled infections or with serious illnesses or medical conditions which would not permit the patient to be managed according to the protocol. This includes but is not limited to:

- known prior history of tuberculosis;

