13 PROTOCOL TREATMENT DISCONTINUATION AND THERAPY AFTER STOPPING

13.1 Criteria for Discontinuing Protocol Treatment

Patients may stop protocol treatment in the following instances:

- Intercurrent illness which would, in the judgement of the investigator, affect assessments of clinical status to a significant degree, and require discontinuation of protocol therapy.
- Unacceptable toxicity as defined in Section 7.5 and Appendix II.
- Disease relapse or new primary invasive malignancy as defined in Section 10.
- Request by the patient.
- Pregnancy or intent to become pregnant
- Initiation of alternative anticancer therapy including another investigational agent.
- Completion of therapy as outlined in Section 7. Efforts should be made to maintain the investigations schedule and continue follow-up, even if patients discontinue protocol treatment prematurely and/or no longer attend the participating institution.

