15.4 Study Endpoints and Analysis

The primary endpoint will be performed on all eligible patients based on patient percentage surgical resection R0 after a maximum of 3 cycles of chemotherapy. It will be presented associated with confidence interval of 95%.

DFS is a secondary endpoint, defined as the time from the date of inclusion to the date of first documented disease relapse or the occurrence of a new invasive primary malignancy or death from any cause. Patients who are alive and disease/new invasive primary malignancy-free at the time of each analysis will be censored at their last disease assessment date.

OS is a secondary endpoint, defined as the time from the inclusion to the date of death of any cause, or censored at their last known alive date. All analysis on DFS will be carried out for the OS endpoint.

The analysis of secondary endpoints will be performed on patient eligible.

Although PD-L1 expression as measured by immunohistochemistry is hypothesized to be a potential predictive marker, this is as yet not validated in either the adjuvant or palliative settings. Further, the cut-off defining PD-L1 positivity has not been validated. This trial will also explore the utility of PD-L1 as a predictive biomarker as well as the optimal cut-off for positivity.

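### The eligible set used for the primary R0 rate has no time limit, so breaches that arise after inclusion can take failures out of the denominator

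*Protocol*

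**What the plan says.** Protocol section 15.4 sets the primary analysis population: "The primary endpoint will be performed on all eligible patients". Section 15.3 defines that population: "The population of eligible patients will consist of ITT patients presenting no deviation judged major on the criteria for inclusion and non-inclusion". The same section has the principal investigators sort deviations into minor and major. It does not say when they do this, or whether they know the surgical result. Section 15.1 describes the trial as unblinded and single-arm. Section 15.3 also defines an ITT set, but 15.4 assigns neither the primary nor the secondary endpoints to it.

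Some entry criteria describe conduct that continues after entry. Section 5.1, criterion 4, reads: "Pre-operative (neo-adjuvant) platinum based or other chemotherapy except the treatment of the protocol is not permissible". It bars pre-operative radiation as well. Criterion 11 requires protocol treatment to start within 7 days of inclusion. Section 10.1 states that patients who had only a segmentectomy or wedge resection are not eligible.

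Section 13.1 lists, among the reasons to stop protocol treatment, the patient's request and "Initiation of alternative anticancer therapy including another investigational agent".

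**The concern.** Section 1.2 gives the first endpoint as the feasibility of complete resection. For such an endpoint, a patient who is included but never starts, goes over to another pre-operative therapy or leaves before surgery has not achieved the outcome. If the same event can also be classed as a major deviation on an inclusion criterion, 15.3 removes the patient instead of counting a failure.

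Removal on this ground would fall mostly on patients without a complete resection, so the R0 percentage would be biased upward. The decision would lie with investigators who may already know the result. Comparability would suffer as well, because the footnote to Table 1 says that its reference rates, including the 91.6% on which the protocol leans, use all patients included in the neoadjuvant arm.

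**Working it through.** **Can the criteria be broken after inclusion?**

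- Criterion 11: yes, and only then, since its clock starts at inclusion.
- Criterion 4: before or after. It exempts protocol treatment, which is given after inclusion. The exemption has a purpose only if the ban runs up to surgery.
- Section 10.1 is not one of the numbered criteria, so 15.3 does not strictly reach it. It does show the protocol using the word eligible for a fact known only at surgery. A limited resection may have clear margins, so removing such a patient does not always remove a failure.

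**Inputs (section 15.2).** "P0 =85%; P1 = 95%; statistical power of 0.90; type I error rate (one-sided) of 0.05". Stage 1: "If there are 34 or fewer responses in these 39 patients, the study will be stopped for futility". The null hypothesis is rejected with at least 71 R0 resections in 77 patients. A 5% allowance for ineligible patients gives 77 × 1.05 = 80.85, hence 81 included. Up to 81 − 77 = 4 patients can therefore leave the set with 77 still analysed.

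**The plan's own figures.** Single-stage, P(X ≥ 71 | n = 77) is 0.045 at p = 0.85 and 0.910 at p = 0.95. With the futility look, the sum over x = 35 to 39 of P(X1 = x | 39) × P(X2 ≥ 71 − x | 38) is 0.042 at 0.85 and 0.895 at 0.95. The stated design reproduces.

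**Effect of removed failures.** The success rule is a count, so deleting a failure does not by itself bring the count nearer to 71. The error rises when the removed patient is made up by another among the 81 and 77 are still analysed. With k failures removed out of 77 + k included, the single-stage error is P(X ≥ 71 | n = 77 + k, p = 0.85):

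| Failures removed (k) | Included | P(reject) at 85% | 71 R0 as a share of included |
|---|---|---|---|
| 0 | 77 | 0.045 | 92.2% |
| 1 | 78 | 0.085 | 91.0% |
| 2 | 79 | 0.144 | 89.9% |
| 3 | 80 | 0.221 | 88.8% |
| 4 | 81 | 0.314 | 87.7% |

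At a true rate of 85%, 81 patients are expected to include 0.15 × 81 = 12.15 failures, so four removals are about a third of them.

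**Two-stage check.** With stage sizes 39 + k1 and 38 + k2 and the same cut-offs, the error is 0.132 for one removal per stage and 0.287 for two per stage.

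**As a share.** If each failure is removed with probability q, the apparent rate is 0.85 / (0.85 + 0.15 × (1 − q)). The two-stage rule on 77 analysed patients then gives:

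- q = 5%: apparent rate 85.6%, error 0.057
- q = 10%: 86.3%, 0.077
- q = 20%: 87.6%, 0.137
- q = 30%: 89.0%, 0.231

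The numbers and shares removed are assumptions. The protocol gives no rate of switching, withdrawal or reclassification.

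**The case against.** The protocol ties eligibility to entry in several places. Section 5.1 speaks of requirements at the time of inclusion. Sections 5.1 and 5.2 both refer to admission to the study. Section 6 has inclusion validated in advance. Later therapy has its own rules: 8.8.2 prohibits concurrent anti-cancer treatment, and 13.1 treats a switch as a reason to stop protocol treatment while asking that follow-up continue. On this reading, a patient who switches breaches section 8 or stops under section 13, neither of which is an inclusion criterion, and so stays in the denominator. Removal also needs a deviation judged major.

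Much of this stands. A reader might infer that the protocol definitely drops treatment failures through criteria that can only be broken after inclusion. The documents do not support that. Criterion 4 can be failed before entry. So can non-inclusion criterion 8, "Concurrent treatment with other investigational drugs or anti-cancer therapy", which bears most naturally on entry given that 8.8.2 covers the treatment period. Inclusion criterion 10, "Patients must be accessible for treatment and follow-up", goes on to ask investigators to assure themselves of availability, which is a judgement made at entry. Of the numbered criteria discussed here, only 11 is confined to the time after inclusion.

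The entry-only reading is nevertheless not written into 15.3. Criteria 4 and 11 and the usage in 10.1 run against it, and the choice is left to an open judgement. Detailed deviation rules may sit in a statistical analysis plan, but the protocol itself fixes the primary population and its definition.

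**Conclusion.** The concern holds as a loosely drawn population rule, not as proof that failures will be removed. Read literally, 15.3 can exclude patients who never start treatment or who switch therapy. With the usage in 10.1, it may also exclude patients who had a limited resection. Nothing in 15.3 prevents the classification from being made with the surgical result known.

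The stated sample size and decision rule are sound when the 77 analysed patients are not selected on outcome. The inflation from 0.045 to between 0.085 and 0.314 rests on three assumptions: all removed patients are not R0, one to four are removed, and they are made up within the 81 so that 77 are analysed. It shows how sensitive the test is and is not a forecast. Even a single such removal takes the one-sided error above the stated 5%.

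**What to change.** In section 15.3:

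- judge eligibility only on facts dated on or before inclusion, and classify deviations without knowledge of the surgical result;
- keep every other included patient in the primary denominator, counting those without an R0 resection after protocol treatment as not R0;
- state how a limited resection with clear margins is counted, so that 10.1 does not work as a hidden exclusion.

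In 15.4, report the ITT R0 rate beside the primary one, which also matches the basis of Table 1.

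The cut-off of 71 belongs to 77 analysed patients. If fewer are removed and more than 77 are analysed, the cut-off must follow the number. For all 81, the single-stage exact cut-off is 75, with error 0.031 and power 0.889.

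The cost is a few sentences and no new data. The observed R0 rate may be slightly less favourable.

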15.4 Study Endpoints and Analysis

The primary endpoint will be performed on all eligible patients based on patient percentage surgical resection R0 after a maximum of 3 cycles of chemotherapy. It will be presented associated with confidence interval of 95%.

DFS is a secondary endpoint, defined as the time from the date of inclusion to the date of first documented disease relapse or the occurrence of a new invasive primary malignancy or death from any cause. Patients who are alive and disease/new invasive primary malignancy-free at the time of each analysis will be censored at their last disease assessment date.

OS is a secondary endpoint, defined as the time from the inclusion to the date of death of any cause, or censored at their last known alive date. All analysis on DFS will be carried out for the OS endpoint.

The analysis of secondary endpoints will be performed on patient eligible.

Although PD-L1 expression as measured by immunohistochemistry is hypothesized to be a potential predictive marker, this is as yet not validated in either the adjuvant or palliative settings. Further, the cut-off defining PD-L1 positivity has not been validated. This trial will also explore the utility of PD-L1 as a predictive biomarker as well as the optimal cut-off for positivity.

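### The final rejection rule (71 or more of 77) fits the primary analysis set only if exactly 77 patients are eligible, and eligibility need not be judged blind to the resection result

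*Protocol*

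**What the plan says.** Section 15.2 sets P0 = 85%, P1 = 95%, power 0.90 and one-sided type I error 0.05. The trial stops for futility at 34 or fewer complete resections in the first 39 patients. At the end, "The null hypothesis will be rejected if 71 or more responses are observed in 77 patients". The next sentence adds: "To take into account 5% of ineligible patients, 81 patients will be included".

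Section 15.4 fixes the analysis set: "The primary endpoint will be performed on all eligible patients". It does not restrict this to the first 77 eligible. Of the result it says "It will be presented associated with confidence interval of 95" percent.

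Section 15.3 defines the eligible set as "ITT patients presenting no deviation judged major on the criteria for inclusion and non-inclusion", and continues: "The deviations to the protocol will be reviewed by the principal investigators and then classified into minor or major deviations". It gives neither the timing of that review nor any requirement that it be done without the surgical outcome. Section 15.1 describes the masking: "This is a multi-centre, prospective unblinded, single-arm phase II trial".

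Two safeguards act at entry. Section 5.1 states: "There will be NO EXCEPTIONS to eligibility requirements at the time of inclusion". Section 6 has sites send the imaging reports before inclusion and has each inclusion validated.

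Section 10.1 also calls patients who had only a segmentectomy or wedge resection not eligible. That is known only after surgery.

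**The concern.** The protocol fixes both a decision threshold and the population to which it applies, and the two agree only at one size of that population. At any other number eligible, the reader must decide whether 71 stays, is scaled, or is recalculated. The trial's conclusion can turn on that choice, because the rule allows only six failures in 77.

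The second issue concerns who is in the set. With so few failures allowed, moving one or two patients between major and minor deviation can change the result. The people who classify may already know whether each resection was complete.

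**Working it through.** **Inputs (15.2):** P0 = 0.85, P1 = 0.95; stop if 34 or fewer of 39; reject if 71 or more of 77; 81 included; 5% ineligible.

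**Formula.** For n eligible and cut-off r, the exact two-stage probability of rejection is the sum over x = 35 to 39 of P(X1 = x) × P(X2 ≥ r − x), with X1 ~ Bin(39, p) and X2 ~ Bin(n − 39, p). Taking p = 0.85 gives alpha and p = 0.95 gives power. The 39 stage 1 patients are taken as eligible.

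**The plan's own figure.** At n = 77 and r = 71, alpha is 0.0423 and power 0.895. With r = 70, alpha would be 0.079, so 71 is the smallest valid cut-off. For the inflation, 77 × 1.05 = 80.85, giving 81. The rule at 77 is sound.

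**How often 77 occurs.** With each of 81 patients independently ineligible with probability 0.05, the number eligible is Bin(81, 0.95): P(77) = 0.200, P(more than 77) = 0.419, P(fewer than 77) = 0.381.

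**Two ways to proceed at other numbers:**

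| Eligible | 71 kept: alpha / power | Smallest r with alpha ≤ 0.05 | Reset: alpha / power |
|---|---|---|---|
| 75 | 0.008 / 0.679 | 70 | 0.023 / 0.823 |
| 76 | 0.021 / 0.816 | 70 | 0.046 / 0.899 |
| 77 | 0.042 / 0.895 | 71 | 0.042 / 0.895 |
| 78 | 0.073 / 0.933 | 72 | 0.039 / 0.891 |
| 79 | 0.111 / 0.949 | 73 | 0.035 / 0.886 |
| 80 | 0.151 / 0.954 | 74 | 0.032 / 0.881 |
| 81 | 0.188 / 0.956 | 75 | 0.030 / 0.877 |

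From 74 down to 68 eligible, the reset cut-offs are 69, 68, 67, 66, 65, 64 and 63, with alpha 0.025 to 0.045 and power 0.830 to 0.869. The range 68 to 81 covers more than 0.999 of cases at 5% ineligible.

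Averaged over the number eligible, keeping 71 gives alpha 0.056 and power 0.82. Resetting gives alpha 0.037 and power 0.878.

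**Dependence on stage 1.** With no futility stop at all, the reset cut-offs have alpha at most 0.0497 (at n = 76). A futility stop can only lower alpha. The cut-offs therefore hold whichever 39 patients were used at stage 1.

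**Outcome-related exclusion (illustration; the ratio is assumed).** Suppose 5% are excluded overall and failures are r times as likely as successes to be excluded. At a true rate of 85%, the exclusion probability for successes is e = 0.05 / (0.85 + 0.15r), and the success rate among the eligible is 0.85(1 − e) / 0.95.
- r = 2: e = 0.0435, rate 0.8558, alpha with reset cut-offs 0.049.
- r = 3: e = 0.0385, rate 0.8603, alpha 0.060.
- Alpha reaches 0.05 at r of about 2.1.

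**The case against.** The strongest reply is that 15.2 and 15.4 do not contradict each other. The design aims at 77 eligible, includes 81 to get there, and analyses those eligible; adjusting a cut-off to the achieved number is normal SAP content, and the SAP is not shown. Much of this stands. A reader might infer from the table that the trial runs at a type I error of 7% to 19%. The document does not support that, because nowhere does it apply 71 to another denominator. Since 15.4 states the endpoint as a percentage, an analyst could as well scale 71/77 and round up. From 68 to 81 eligible, that gives the reset cut-offs everywhere except at 76 (71 instead of 70), with alpha never above 0.045.

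A reader might also take the 95% confidence interval as a competing decision rule. It is not one. The text only presents it with the estimate, and a two-sided 95% interval ordinarily differs from a one-sided 5% test.

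On eligibility, exclusions are confined to entry criteria, which are mostly pre-treatment facts, and sections 5.1 and 6 screen patients before inclusion. This makes late exclusions fewer but leaves the later major/minor classification open to knowledge of outcome. Fewer exclusions also push the number eligible above 77, where an unchanged 71 would be too lenient.

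**Conclusion.** The point holds as a mismatch that is cheap to repair, not as a demonstrated alpha error. The stated threshold matches the stated analysis set in about one case in five, assuming independent 5% ineligibility. Elsewhere the protocol leaves the decision rule open. If 71 were carried over, the average excess in alpha would be small (0.056 against 0.05) and the loss of power larger (0.82 against 0.90); at 78 or more eligible, the alpha excess would be material. With reset cut-offs, alpha is at most 0.046 for 68 to 81 eligible, and average power is about 0.88.

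The exposure of the eligibility judgement to the resection result is a real weakness of unknown size. A reader might infer that the result will be biased; nothing in the protocol shows this. On the illustration above, failures would have to be excluded about twice as often as successes before reset alpha passed 5%.

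The 10.1 sentence is a matter of clarity only. Section 15.3 ties eligibility to entry criteria, and a limited resection could meet the complete-resection definition in 11.1.1. Removing such a patient would take away a success, so it would not inflate alpha.

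**What to change.** - **15.2 and 15.4:** keep the eligible set as primary. State that the final test uses the smallest cut-off with exact one-sided alpha at most 5% at the achieved number eligible, for example 75:70, 76:70, 77:71, 78:72, 79:73, 80:74, 81:75. Restate power as about 88% on average at 5% ineligibility (about 0.82 to 0.90 by number eligible). Say that the 95% interval is descriptive.
- **Timing:** 15.5 places the restart at the 46th patient, so stage 1 may already have been assessed. Keep any stage 1 decision, and the 39 patients behind it, as applied. Record that the final cut-offs were set without sight of resection results; they depend only on the number eligible.
- **15.3:** state that major eligibility deviations are judged on pre-treatment data only, from listings without surgical results. Report the ITT set already defined there as a sensitivity analysis, counting patients not operated on, or with R1 or R2, as not completely resected.
- **10.1:** reconcile the segmentectomy/wedge sentence with 15.3 and 11.1.1, so that it is clear whether the operation performed affects membership of the primary set.

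Cost: wording in four sections, stated power about two points lower, and slightly more data-review work. There are no extra patients and no change of primary population.
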